 - The subject must have been diagnosed with episodic migraine headache at least six months prior to entering into the Study, consistent with the International Headache Classification of Headache Disorders (ICHD-II and ICHD-III beta) guidelines.
 - The subject must have a history of at least three consecutive months of stable migraine headaches prior to entering the study. The subjects will not have had changes in medication usage (prescription medications for migraine headache) for the three months leading up to the study, nor will they introduce new medications during the study period. (The primary focus is on prescription medications for migraine headache. However, medications that are prescribed for co-morbid conditions which also have

demonstrated efficacy for migraine prevention should not be altered in this time period.)

- Subjects will satisfy these criteria: On a monthly basis, at least four, and not more than a total of fourteen (4-14), headache days of which between four and fourteen (4-14) are migraine headache days, as judged by the subject.
- The subject must not have failed on more than two classes of properly administered prophylactic pharmaceutical therapies for migraine headache. The subject may be on a single migraine prophylactic drug as long as the dosage has not been altered within three months of starting the study and the dosage must not be altered for the duration of the study;
- The Investigator must have confidence in the subject's ability to reliably use the CVS device and promptly complete the electronic daily headache diary forms. The daily headache diary will be completed from the beginning of the pre-treatment baseline period through the end of the study. The diary is described more fully below and in the definitions section at the end of this document.

• **Exclusion Criteria:** Individuals who:

- have previously participated in a clinical trial using the CVS Device
- are pregnant
- using more than one concurrent prophylactic pharmaceutical therapy for migraine headache
- have a history of cardiovascular disease
- work night shifts
- have been diagnosed with vestibular migraine
- have menstrual migraine exclusively
- have been diagnosed with post-traumatic migraine
- have a history of unstable mood disorder or unstable anxiety disorder. Specifically, a BDI-II score of 20 or greater and/or a BAI score of 16 or greater will disqualify a patient from randomizing into the treatment portion of the study.
- use a hearing aid

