- have a cochlear implant
- have chronic tinnitus
- have temporomandibular joint disease
- have been diagnosed with traumatic brain injury
- have been diagnosed with neurological disease other than headaches

- have a diagnosed vestibular dysfunction and/or balance dysfunction
- have a history of abusing alcohol or other drugs
- are experiencing medication overuse headaches (individuals with respect to whom the principal investigator is concerned that analgesic abuse is involved based on the ICHD-II guidelines).
- are less than 18 years old or greater than 65 years old
- have had eye surgery within the previous three months or ear surgery within the previous six months
- have active ear infections or a perforated tympanic membrane
- have participated in another clinical trial within the last 30 days or are currently enrolled in another clinical trial
- are using Botulinum toxin-based treatments for migraines or for facial cosmetic reasons.
- are taking anti-emetics chronically (more than 2 times per week, consistently)
- Though not excluded, subjects taking anti-histamines will be encouraged not to take such medications within four hours prior to a CVS treatment. The investigator should review other medications taken by the subject with properties that mimic anti-nausea or anti-dizziness drugs as these may reduce responsiveness of the vestibular system to caloric stimulation. Such medications should also be avoided within four hours prior to a CVS treatment.

- **Withdrawal Criteria**

- Subjects must be withdrawn from the clinical trial if any of the following events occur:
 - Surgery during the study period.
 - A subject does not continue to meet inclusion/exclusion criteria.
 - A subject is significantly non-compliant with the requirements of the protocol (principal investigator & sponsor decision).
 - The subject does not complete at least 25 of 28 daily diary entries in her/his headache diary during the baseline period. (That is, the subject must be compliant with maintaining the headache diary.)
 - A subject becomes pregnant during the trial as evidenced by a positive pregnancy test.
 - The subject develops an illness (adverse event) that would interfere with his/her continued participation.
 - The subject withdraws his/her consent.
 - The principal investigator feels that it is the subject's best interest to be withdrawn.
 - Scion Neurostim discontinues the study or has achieved the targeted enrollment.

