- (iii) Also, women of childbearing age will complete a urine-based pregnancy test to reconfirm that they are not pregnant. The unblinded coordinator will open, at random, an envelope assigning the subject to one of the three study arms. The clinic period is described below. During the first visit, the subject will complete a training session based on a set training module. The subject will complete a proficiency evaluation and the study coordinator will certify the subject's proficiency in the use of the CVS device. The study coordinator will

complete a visit assessment form. At the end of training, a first usability questionnaire will be completed by the subject.

(iv) **First Treatment Period:** The eighty-four days (3 months) following the pre-treatment baseline period constitute the first treatment period. This is the test period, the results from which will be measured against the pre-treatment baseline period data in assessing the study endpoints. Specifically, data from the last month of the first treatment period will be compared with the one-month-long pre-treatment baseline period. As close as possible (as scheduling permits) to two weeks after the start of treatment, a clinical visit will occur and another visit assessment form will be completed. A second usability questionnaire will be completed. The subject will be asked to bring the CVS device to the clinic to perform a treatment in front of the unblinded study coordinator to reaffirm proficiency in using the device. Any issues related to balance or other safety concerns will promptly be referred to the site principal investigator, who can terminate the subject's further participation in the study if necessary.

(v) **End of First Treatment Period – Start of Second Treatment Period:** At the end of the first treatment period the subject will be asked to return to the clinic and will be asked to complete the QOL questionnaires and a third usability questionnaire. All subjects will receive new SD cards for the second treatment period and the old SD cards will be retained so that treatment compliance logs can be extracted. All subjects will receive active treatment cards with the following assignments (first treatment period -> second treatment period):

- BID placebo -> BID active
- BID active -> BID active
- QD active -> QD active

Subjects will perform a treatment in front of the unblinded coordinator to re- confirm their ability to properly use the device.

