PROTOCOL NUMBER: _____**Treatment Day 1 (Visit 2)****Baseline Daily Headache Diary:****Yes** **No**

Does the subject have on a monthly basis, at least four, and not more than a total of fourteen (4-14), headache days of which between four and fourteen (4-14) are migraine headache days, as judged by the subject.		
If Yes , please proceed with Treatment Day 1 Visit procedures. If No , please conclude the visit, and complete the Subject Disposition Form. Subject is a Screen Failure.		

Adverse Events and Concomitant Medication Assessment:**Yes** **No**

Any Adverse Events (AEs) since last visit?		
If Yes , please complete AE form.		
Any new medications or changes in medications since last visit?		
If Yes , please add medication(s) to the Concomitant Medication form. Acute abortive medications and migraine prophylactic medications should not be changed during the clinical trial.		

Vital Signs:

Height:	_____ cm / inches (circle one)
Weight:	_____ kg / lbs (circle one)

Urine Pregnancy Test Results:**Positive** **Negative** **N/A**

Name:	Lot #:	Exp. Date:			
-------	--------	------------	--------------------------	--------------------------	--------------------------

Ear Exam: Observations and check for presence of cerumen (recommend cleaning procedure as needed). _____

Physician Signature (for ear exam): _____ **Date:** _____

Quality of Life Assessments:**Yes** **No****Scores**

Hit-6 Questionnaire (completed)			
Pittsburgh Sleep Quality Assessment (completed)			
BDI-II (completed)			
BAI (completed)			
A BDI-II score of 20 or greater and/or a BAI score of 16 or greater will disqualify a patient from randomizing into the treatment portion of the study.			

Randomization:**Yes** **No**

Does the subject met all eligibility criteria for randomization?		

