If Yes , please proceed with Device Treatment Training. If No , please conclude the visit, and complete the Subject Disposition Form. Subject is a Screen Failure.		

SUBJECT ID: _____
DATE: _____SITE #: _____
PROTOCOL NUMBER: _____**Device Treatment at the Clinical Site:****Yes** **No**

Any side effects or AEs reported after device treatment?		
Was the device treatment aborted?		
Any complaints from subject?		
Any concerns about the subject?		
If Yes, to any questions above, please provide comment:		

- Dispense TNM Device to subject.
- Review device compliance and proper operation of the device and delivery of treatments.
- Administer Usability Questionnaire after completion of device training.
- Review Daily Headache Diary completion and upload to gmail account each day.

Study Coordinator: *I verify that the subject has received training and has shown competence in using the TNM Device. I believe that the subject will be able to complete device treatments in the home setting. I have confirmed with the subject that he/she will contact me regarding any future questions regarding safe use of the TNM device, should they arise.*

Study Coordinator Signature_____
Date

I have reviewed the data from this visit and found the information to be complete and accurate. I verify that all of the tasks have been performed.

Principal Investigator Signature_____
Date

SUBJECT ID: _____
DATE: _____SITE #: _____
PROTOCOL NUMBER: _____**Clinic Visit Day 14 (Visit 3)****Adverse Events and Concomitant Medication Assessment:** Yes No

Any Adverse Events (AEs) since last visit?		
If Yes, please complete AE form.		
Any new medications or changes in medications since last visit?		
If Yes, please add medication(s) to the Concomitant Medication form. Acute abortive medications and migraine prophylactic medications should not be changed during the clinical trial.		

Ear Exam: Observations and check for presence of cerumen (recommend cleaning procedure as needed). _____

Physician Signature (for ear exam): _____ **Date:** _____

Vital Signs:

Height:	_____ cm / inches
Weight:	_____ kg / lbs

Device Treatment at the Clinical Site:

Yes No

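### Device training and proficiency certification come after randomisation, and the plan does not say what happens to a randomised subject who is not certified

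*Combined protocol and SAP*

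**What the plan says.** **Order of steps.** In section 4 (Study Schedule; Subject Enrollment and Activities), item (iii), the envelope comes straight after the pregnancy test: "The unblinded coordinator will open, at random, an envelope assigning the subject to one of the three study arms". Training comes next: "During the first visit, the subject will complete a training session based on a set training module". Then comes the check: "The subject will complete a proficiency evaluation and the study coordinator will certify the subject's proficiency in the use of the CVS device". No pass mark is given, and no consequence of failing.

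The Treatment Day 1 (Visit 2) form follows the same order. Under Randomization it asks "Does the subject met all eligibility criteria for randomization" and, if the answer is yes, directs the site: "please proceed with Device Treatment Training". Next is the block on device treatment at the site, which records side effects, aborted treatment, complaints and concerns about the subject. Only below that does the coordinator sign: "I verify that the subject has received training and has shown competence in using the TNM Device". The coordinator also signs a belief that the subject can complete treatments at home.

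**Entry and withdrawal.** The Inclusion Criteria in section 2 contain one item on device use: "The Investigator must have confidence in the subject's ability to reliably use the CVS device". The same item covers prompt completion of the diary. The criteria are judged at initial screening by the principal investigator or a designee. Section 4(ii) has the investigator reconfirm participation before the training visit. The Withdrawal Criteria require removal in this case: "A subject does not continue to meet inclusion/exclusion criteria".

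**Analysis.** Section 8 calls the primary analysis intent-to-treat, but performs it on subjects with at least 25 diary entries in the relevant 28-day month.

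**The concern.** One inclusion item names two abilities, and the plan tests them at different times. Diary ability is verified at screening and then tested by the 25-of-28 rule before randomisation. Device ability is tested only after the arm has been assigned. The investigator's confidence at screening and at reconfirmation therefore rests on no observed use of the device; the Schedule of Visits and Procedures first marks device training on Treatment Day 1.

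Three things follow. A competence judgement made after allocation can be influenced by knowledge of the arm. If it is made in the order the form prints, it can also be influenced by how the session went, and sessions differ by arm: section 5 gives active subjects warm and cold waveforms and leaves the sham earpieces unpowered. Finally, a randomised subject who is not certified has no defined status. If that subject leaves, month-three diaries are missing and the subject drops out of the primary comparison. This is avoidable selection after randomisation, and it would favour the active arm if such losses fell there.

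**Working it through.** **1. The plan's own figure.** Inputs from section 8: 40 per arm, SD 3.36 days, alpha 0.05, power 80%, detectable difference 2.13 days. A two-sided two-sample t calculation gives a detectable difference of 2.131 days, and power of 79.95% at 2.13 days. The stated figure is reproduced. The fix below changes only the order of steps, so sample size, alpha and power stay as planned. Section 3 also sets the target as up to 120 subjects who complete the first treatment period, so early losses can be replaced. The question is therefore bias rather than power.

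**2. How a subject could be lost.** The steps are:
- the subject is randomised, trained and not certified (section 4(iii) and the Visit 2 form);
- the investigator may then lose confidence in the subject's ability, so the inclusion item is no longer met (section 2);
- the subject may be withdrawn (Withdrawal Criteria), with final-visit evaluations to be attempted but no continued diary on the Early Termination Visit form;
- fewer than 25 entries exist for month three, so the subject is not analysed (section 8).

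The documents permit each step. None of them states the whole chain.

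**3. Size of the bias under assumed losses.** No failure rate is given, so the number lost, k, is an assumption.

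Inputs:
- 45 randomised to twice-daily active: 40 completers plus the 5 dropouts per group expected in each three-month period (section 8);
- mean reduction among those kept, 3.6 days: the active result in the previous trial (Background);
- mean reduction m that the lost subjects would have had: 0 days (extreme), or 0.9 days (the placebo result in the previous trial);
- no losses of this kind in the sham arm.

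The mean over all 45 is [(45 − k) × 3.6 + k × m] / 45. The mean over those kept is 3.6. The overstatement is the difference, (k / 45) × (3.6 − m).

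| k | m = 0 | share of 2.73 | m = 0.9 | share of 2.73 |
|---|---|---|---|---|
| 2 | 2/45 × 3.6 = 0.16 | 6% | 2/45 × 2.7 = 0.12 | 4% |
| 4 | 4/45 × 3.6 = 0.32 | 12% | 4/45 × 2.7 = 0.24 | 9% |
| 6 | 6/45 × 3.6 = 0.48 | 18% | 6/45 × 2.7 = 0.36 | 13% |

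The divisor, 2.73 days, is the effect from the previous trial that section 8 cites. The row k = 6 exceeds the 5 dropouts per group expected from all causes in the period and leaves 39 of 45, so it is the outer edge. If k = 0, the overstatement is zero.

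**The case against.** A reader might infer that an entry condition is being judged after allocation. The documents do not support that. The written condition is the investigator's confidence, judged at screening, reconfirmed before the training visit, and covered by the eligibility question on the Visit 2 form before training starts. Certification is a separate training check made by a coordinator, and it is nowhere listed as an entry criterion.

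A reader might also infer that an uncertified subject must be withdrawn. No text says so. The form's gates before training carry a screen-failure consequence; after training it offers only a comment box and a sign-off. Withdrawal is possible, but only if failed certification is taken to mean lost investigator confidence.

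Nor do the documents say that the certifier is unblinded. Section 4(iii) says only the study coordinator. The inference is well supported, because an unblinded coordinator opens the envelope at the same visit and an unblinded coordinator rechecks proficiency at two weeks. That the session precedes certification comes from the layout of the form, not from section 4(iii).

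The strongest objection is to the mechanism. Handling should not differ by arm: section 5 says the devices look identical and show the same progress plot, so handling failures should be similar across arms. Losses confined to the active arm would more plausibly come from poor tolerance of the session, and a handling test without a waveform cannot detect that. The missing-diary problem also affects every post-randomisation dropout, whatever the order of training.

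All of this stands, and it limits the claim. It does not remove the two defects in the text: the competence check sits after allocation for no stated reason, and its failure has no stated consequence.

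**Conclusion.** The point holds as a cheap improvement to the sequence and as a gap in the rules. It does not show a bias. Ability to use the device is first tested after allocation, apparently by someone who may know the arm, and the plan is silent on a subject who fails. The withdrawal rule and the 25-entry rule could together remove such a subject from an analysis labelled intent-to-treat.

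The range of 0.12 to 0.48 days is a one-sided worst case. It rests on assumed numbers of failures, all in the active arm, and on an assumed poor outcome for the subjects lost. The true effect may be zero.

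**What to change.** In section 4(iii) and on the Visit 2 form, move device-handling training and the proficiency evaluation (unpacking, headset fit, touchscreen steps, pillow position) ahead of the envelope, with no waveform run. Open the envelope only for certified subjects, and hold the in-clinic session on the assigned device afterwards.

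Add a sentence to section 4 and section 8: proficiency problems found after allocation, including at the two-week visit, are recorded and reported by arm, and do not by themselves end diary follow-up or remove the subject from the intent-to-treat set.

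The cost is a reordering within one existing visit and an edit to one form. A small downside is that certification rests on handling rather than on a live session. The reordering will not keep subjects who leave because they cannot tolerate the active session; only continued diary follow-up addresses that, which is why the added sentence is needed as well.
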